14.5 Interim Analysis

Every 6 weeks:

- Information will be shared with the UCSF IRB.

Every 3 months:

- An interim analysis will be conducted and reported or after the 10th subject is recruited

14.6 Sample Size and Randomization

One primary outcome is the difference in VHI-10 score at 6 weeks after injection with DAXI. The normative values of the VHI-10 have been established, with a normal value of 2.83 and standard deviation of 3.93. One prospective study for Botox in SD determined a pretreatment VHI-10 score of 22.58 +/- 7.09 and 6-week post-treatment 20.86 +/- 7.24. The difference had a standard deviation of approximately 10. A sample size of 20 will provide 80% power to detect a difference of 6.6 at a significance threshold (alpha) of 0.05.

A secondary outcome will be comparing the duration of effect of DAXI with patients' prior Botox treatment. Specifically, we will determine the median time to baseline VHI-10 after treatment with DAXI and produce a Kaplan-Meier curve to illustrate the duration of clinical benefit. A large retrospective study from Blitzer et al from described the average duration of benefit to be about 15.1 weeks with a standard deviation of 12.3 weeks [10]. Unpublished data from our institution revealed an average duration of 18.9 weeks with a standard deviation of 7.2 weeks. Using the data from our institution, a sample size of 20 will provide 80% power to detect a difference in average duration of 2.4 weeks. (This calculation assumed a with-subject correlation coefficient of 0.875.)

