5 CRITERIA FOR EVALUATION

5.1 Primary Efficacy Endpoint

The primary efficacy endpoint is the difference in VHI-10 scores at 8 weeks after injection with DAXI. VHI-10 questionnaires will be given at baseline, day 14, then monthly.

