9.5 Visit 4 (Phone call, Day 14*)

1. Phone call to assess clinical improvement
2. Ensure there is absence of dysphagia (using EAT-10 questionnaire), no injection site issue, or other adverse event

*Day 14 after most recent DAXI injection

9.6 Visits 5-10 (Remote Survey, every month starting 1 month after most recent injection)

1. Phone call to assess duration of benefit
2. Patient fills out PROMs electronically through Qualtrics to assess our primary (VHI-10) and secondary outcome measures

- VHI-10
 - CPIB-10
 - OMNI-VES
 - EAT-10
3. Patient records their voice in Phonalyze for CPP and CAPE-V analysis
 4. Patient will record whether DAXI still has desired effect

Data is collected monthly until loss of benefit.

For every instance when all PROMs and Phonalyze recordings are completed, patients will be paid \$10, up to \$150. After the completion of the study the number of entries will be tabulated and patient will be given a Visa gift card in the allotted amount. Patients who withdraw from the study will still be compensated for all instances when PROMs and Phonalyze recordings were completed.

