11.3 Replacement of Participants

N/A

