14.3 Analysis of Primary Endpoint

Our primary outcome is the difference in VHI-10 score at 8 weeks after injection with DAXI. This will be determined using a paired t-test with subjects pre-treatment VHI-10 scores as a control. Our second primary outcome measure is the duration of effect of DAXI, assessed qualitatively through phone calls, compared to patients' prior Botox treatment. We will produce a Kaplan-Meier curve to illustrate the duration of clinical benefit after treatment with DAXI.

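### The 80% power statement refers to a 6-week VHI-10 that is not scheduled, the primary is at 8 weeks with no named visit or starting injection, and the power needs 20 complete pairs

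*Combined protocol and SAP*

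**What the plan says.** Section 5.1: "The primary efficacy endpoint is the difference in VHI-10 scores at 8 weeks after injection with DAXI". Section 14.3 repeats the time point, "Our primary outcome is the difference in VHI-10 score at 8 weeks after injection with DAXI", and specifies a paired t-test against the pre-treatment score.

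Section 14.6, which justifies the sample size, says instead: "One primary outcome is the difference in VHI-10 score at 6 weeks after injection with DAXI". It quotes a Botox study with VHI-10 of 22.58 (SD 7.09) before treatment and 20.86 (SD 7.24) at 6 weeks, adds "The difference had a standard deviation of approximately 10", and concludes that 20 subjects give 80% power for a difference of 6.6 at alpha 0.05. The synopsis repeats that power figure without a time point.

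On collection, section 5.1 says: "VHI-10 questionnaires will be given at baseline, day 14, then monthly". Section 9.6 anchors the monthly surveys (Visits 5-10): "every month starting 1 month after most recent injection". Sections 5.2 and 9.6 and Appendix 1 continue them only until benefit is lost. In Appendix 1 the footnote giving a window of ±2 days is attached to Visits 1-4, not to Visits 5-10. A second injection is possible at Visit 3, day 7-14 (section 9.4).

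Section 4.1 plans 20 subjects. Section 11.3, on replacement, reads N/A, and section 14.6 makes no allowance for loss.

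**The concern.** The power statement is the only planning figure for the primary endpoint. As written, it describes a comparison at a week when no VHI-10 is scheduled, using 6-week data and not saying that these are carried over to week 8.

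The 8-week endpoint is not tied to a visit either. The monthly surveys restart after a second injection and have no window, and neither section 5.1 nor section 14.3 says whether the 8 weeks run from the first or the last injection. For a re-injected subject, more than one survey could be taken as the primary score. The trial is open-label and single-arm, and the investigator team reviews data at least every 2 weeks (section 13), so that choice should be fixed in advance.

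The stated power also rests on two conditions that section 14.6 does not spell out: almost no correlation between a subject's two scores, and a complete pair from every enrolled subject.

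**Working it through.** **1. Reproducing the 80%.** Inputs from section 14.6: n = 20, difference 6.6, SD of the difference 10, alpha 0.05. Two-sided testing is my assumption, since sidedness is not stated. Paired t-test, 19 degrees of freedom:
- noncentrality = (6.6 / 10) × √20 = 2.95; critical value 2.093
- power from the noncentral t = 79.9%
- difference detectable with 80% power = 6.60

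The stated figure reproduces. A one-sided test would give 88.5%, so two-sided is evidently what was meant.

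**2. Where the scheduled scores fall.** Taking a month as 30.4 days, and week 8 as day 56:

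| Case | Month-1 survey | Month-2 survey |
|---|---|---|
| One injection, day 0 | day 30 | day 61 |
| Second injection day 7, counted from first | day 37 | day 68 |
| Second injection day 14, counted from first | day 44 | day 75 |

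Counted from the most recent injection, month 2 (Visit 6) is the survey nearest week 8, about 5 days late (61 − 56). Counted from the first injection, with a second on day 14, month 2 is 19 days late (75 − 56) and month 1 is 12 days early (56 − 44). The anchor therefore decides which score is nearest.

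With a second injection on day 7-14, the month-1 survey falls 37 to 44 days, or about 5.3 to 6.3 weeks, after the first injection. That is a by-product of restarting the schedule, not a planned 6-week assessment.

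**3. What an SD of 10 implies.** For paired scores, SD² of the difference = s₁² + s₂² − 2r·s₁·s₂, with s₁ = 7.09 and s₂ = 7.24:
- s₁² + s₂² = 50.27 + 52.42 = 102.69; 2·s₁·s₂ = 102.66
- r = 0 gives SD = √102.69 = 10.13
- SD = 10 gives r = (102.69 − 100) / 102.66 = 0.03

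**4. Sensitivity to the correlation** (r of 0.25 and 0.5 are assumed; the documents give none for VHI-10), with 20 pairs:

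| r | SD of difference | Power for 6.6 | Detectable at 80% |
|---|---|---|---|
| 0 | 10.13 | 78.9% | 6.7 |
| 0.25 | 8.78 | 89% | 5.8 |
| 0.5 | 7.17 | 97% | 4.7 |

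**5. Sensitivity to complete pairs** (losses are assumed; the documents give no rate), at SD 10 and difference 6.6:

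| Complete pairs | Power |
|---|---|
| 20 | 79.9% |
| 18 | 75% |
| 16 | 69% |

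At r = 0.25, 16 pairs still give 80%.

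No 8-week SD is given, so power at the actual primary time point cannot be computed without assuming that the 6-week SD carries over.

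**The case against.** The strongest defence is that the endpoint definition and the analysis section agree on 8 weeks, and only the planning paragraph differs. The test and N = 20 are unaffected by correcting that paragraph, and the calculation reproduces. All of this stands, and it makes the problem an inconsistency rather than an arithmetic error. It is also true that an unmeasured week 6 cannot be picked after seeing data. The room for choice comes from the undefined anchor and window of the 8-week score.

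Three stronger readings are tempting, and the documents do not support them:
- **That the trial is underpowered.** The two sensitivities pull in opposite directions. Lost pairs lower power, while positive correlation makes SD 10 conservative. Power of 69-75% requires both near-zero correlation and losses that are assumed.
- **That the correlation of 0.875 in the next paragraph of section 14.6 contradicts the SD of 10.** That value concerns duration of effect, DAXI against earlier Botox. It is a different variable and comparison, and nothing requires it to hold for VHI-10 before and after treatment.
- **That the authors wrongly treated the pairs as independent.** Section 14.6 presents the SD as a property of the cited study's difference. The match with 10.13 is suggestive, but whether the SD was reported or derived cannot be checked from these documents.

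Nor should the power be judged against the cited study's own change of 1.72 points (22.58 − 20.86). The plan targets 6.6 and never claims to detect 1.72.

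**Conclusion.** The concern holds as a time-point inconsistency with unstated conditions. Section 14.6 must be reconciled with sections 5.1 and 14.3, because its power statement concerns a 6-week difference that the schedule does not provide. The 8-week primary needs a named visit, an anchoring injection and a window. Without them, month 2 lies about 5 days after week 8 for a single injection and up to about 19 days after it, counted from the first injection, when a second is given on day 14.

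The 80% is right for its own inputs, given two-sided 0.05, SD 10 (r of about 0.03) and 20 complete pairs out of 20 enrolled. The last condition is not secured: there is no allowance for loss, no replacement provision, and a subject whose benefit ends early may have no week-8 score. The range over assumed conditions is 69% (16 pairs, SD 10) to 97% (20 pairs, r = 0.5) for 6.6 points. No larger sample is shown to be necessary.

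**What to change.** 1. Use 8 weeks in sections 5.1, 14.3 and 14.6.
2. In sections 5.1 and 14.3, name the month-2 survey (Visit 6) as the primary assessment. State that it is timed from the most recent DAXI injection, if that is the intent, and give it a window in Appendix 1.
3. Collect the Visit 6 VHI-10 even if benefit has already been lost, and say so in section 9.6 and Appendix 1.
4. Add a sensitivity analysis timed from the first injection, with a rule fixed in advance for which survey counts, since for re-injected subjects it may be month 1 or month 2.
5. In section 14.6, state that the planning SD comes from 6-week data and is assumed to apply at 8 weeks, and that the test is two-sided. Restate power conditionally: 80% for 6.6 points with 20 complete pairs at SD 10; 75% with 18 and 69% with 16 (assumed losses); detectable difference with 20 pairs of 5.8 if the correlation is 0.25 and 4.7 if it is 0.5 (assumed).

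Keep the monthly schedule. Surveys every 28 days would put Visit 6 exactly at week 8, but the sixth survey would then fall at week 24 (6 × 28 = 168 days) instead of about week 26 (6 × 30.4 = 182 days), shortening follow-up for duration of benefit.

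The cost is mostly wording, plus at most one remote questionnaire for subjects who lose benefit before Visit 6. The power becomes a range whose lower end is less favourable than the present single figure.

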15 DATA COLLECTION, RETENTION AND MONITORING

15.1 Data Collection Instruments

The Investigator will prepare and maintain adequate and accurate source documents designed to record all observations and other pertinent data for each subject treated with the study drug.

Study personnel at each site will enter data from source documents corresponding to a subject's visit into the protocol-specific electronic Case Report Form (eCRF) into a REDCap database when the information corresponding to that visit is available. Participants will not be identified by name in the study database or on any study documents to be collected by the Sponsor (or designee), but will be identified by subject number and initials.

If a correction is required for an eCRF, the time and date stamps track the person entering or updating eCRF data and creates an electronic audit trail.

The Investigator is responsible for all information collected on participants enrolled in this study. All data collected during the course of this study must be reviewed and verified for completeness and accuracy by the Investigator.

15.2 Data Management Procedures

The data will be entered into a validated database. The Data Management group will be responsible for data processing, in accordance with procedural documentation. Database lock will occur once quality assurance procedures have been completed.

All procedures for the handling and analysis of data will be conducted using good computing practices meeting FDA guidelines for the handling and analysis of data for clinical trials.

15.3 Data Quality Control and Reporting

After data have been entered into the study database, a system of computerized data validation checks will be implemented and applied to the database on a regular basis. Queries are entered, tracked, and resolved through the REDCap and Qualtrics system directly. The study database will be updated in accordance with the resolved queries. All changes to the study database will be documented.

15.4 Archival of Data

The database is safeguarded against unauthorized access by established security procedures; appropriate backup copies of the database and related software files will be maintained. Databases are backed up by the database administrator in conjunction with any updates or changes to the database.

At critical junctures of the protocol (e.g., production of interim reports and final reports), data for analysis is locked and cleaned per established procedures.

15.5 Availability and Retention of Investigational Records

The Investigator must make study data accessible to the monitor, other authorized representatives of the Sponsor (or designee), IRB/IEC, and Regulatory Agency (e.g., FDA) inspectors upon request. A file for each subject must be maintained that includes the signed Informed Consent & HIPAA Authorization Form and copies of all source documentation related to that subject. The Investigator must ensure the reliability and availability of source documents from which the information on the CRF was derived.

All study documents (patient files, signed informed consent forms, copies of CRFs, Study File Notebook, etc.) must be kept secured for a period of two years following marketing of the investigational product or for two years after centers have been notified that the IND has been discontinued. There may be other circumstances for which the Sponsor is required to maintain study records and, therefore, the Sponsor should be contacted prior to removing study records for any reason.

15.6 Monitoring

Monitoring visits will be conducted by representatives of the Sponsor-Investigator according to the U.S. CFR Title 21 Parts 50, 56, and 312 and ICH Guidelines for GCP (E6). By signing this protocol, the Investigator grants permission to the Sponsor (or designee), and appropriate regulatory authorities to conduct on-site monitoring and/or auditing of all appropriate study documentation.

15.7 Subject Confidentiality

In order to maintain subject confidentiality, only subject number and subject initials will identify all study participants on CRFs and other documentation

submitted to the Sponsor. Additional subject confidentiality issues (if applicable) are covered in the Clinical Study Agreement.

16 ADMINISTRATIVE, ETHICAL, REGULATORY CONSIDERATIONS

The study will be conducted according to the Declaration of Helsinki, Protection of Human Volunteers (21 CFR 50), Institutional Review Boards (21 CFR 56), and Obligations of Clinical Investigators (21 CFR 312).

To maintain confidentiality, all laboratory specimens, evaluation forms, reports and other records will be identified by a coded number and initials only. All study records will be kept in a locked file cabinet and code sheets linking a patient's name to a patient identification number will be stored separately in another locked file cabinet. Clinical information will not be released without written permission of the subject, except as necessary for monitoring by the FDA. The Investigator must also comply with all applicable privacy regulations (e.g., Health Insurance Portability and Accountability Act of 1996, EU Data Protection Directive 95/46/EC).

16.1 Protocol Amendments

Any amendment to the protocol will be written by the Investigator. Protocol amendments cannot be implemented without prior written IRB/IEC approval except as necessary to eliminate immediate safety hazards to patients. A protocol amendment intended to eliminate an apparent immediate hazard to patients may be implemented immediately, provided the IRBs are notified within five working days.

16.2 Institutional Review Boards and Independent Ethics Committees

The protocol and consent form will be reviewed and approved by the IRB/IEC of each participating center prior to study initiation. Serious adverse experiences regardless of causality will be reported to the IRB/IEC in accordance with the standard operating procedures and policies of the IRB/IEC, and the Investigator will keep the IRB/IEC informed as to the progress of the study. The Investigator will obtain assurance of IRB/IEC compliance with regulations.

Any documents that the IRB/IEC may need to fulfill its responsibilities (such as protocol, protocol amendments, Package Insert, consent forms, information concerning patient recruitment, payment or compensation procedures, or other pertinent information) will be submitted to the IRB/IEC. The IRB/IECs written

unconditional approval of the study protocol and the informed consent form will be in the possession of the Investigator before the study is initiated. The IRB/IECs unconditional approval statement will be transmitted by the Investigator to the Sponsor prior to the shipment of study supplies to the site. This approval must refer to the study by exact protocol title and number and should identify the documents reviewed and the date of review.

Protocol and/or informed consent modifications or changes may not be initiated without prior written IRB/IEC approval except when necessary to eliminate immediate hazards to the patients or when the change(s) involves only logistical or administrative aspects of the study. Such modifications will be submitted to the IRB/IEC and written verification that the modification was submitted and subsequently approved should be obtained.

The IRB/IEC must be informed of revisions to other documents originally submitted for review; serious and/or unexpected adverse experiences occurring during the study in accordance with the standard operating procedures and policies of the IRB; new information that may affect adversely the safety of the patients of the conduct of the study; an annual update and/or request for re-approval; and when the study has been completed.

16.3 Informed Consent Form

Informed consent will be obtained in accordance with the Declaration of Helsinki, ICH GCP, US Code of Federal Regulations for Protection of Human Subjects (21 CFR 50.25[a,b], CFR 50.27, and CFR Part 56, Subpart A), the Health Insurance Portability and Accountability Act (HIPAA, if applicable), and local regulations.

The Investigator will prepare the informed consent form and HIPAA authorization and provide the documents to the Sponsor or designee for approval prior to submission to the IRB/IEC. The consent form generated by the Investigator must be acceptable to the Sponsor and be approved by the IRB/IEC. The written consent document will embody the elements of informed consent as described in the International Conference on Harmonisation and will also comply with local regulations. The Investigator will send an IRB/IEC-approved copy of the Informed Consent Form to the Sponsor (or designee) for the study file.

A properly executed, written, informed consent will be obtained from each subject prior to entering the subject into the trial. Information should be given in both oral and written form and subjects (or their legal representatives) must be

given ample opportunity to inquire about details of the study. If a subject is unable to sign the informed consent form (ICF) and the HIPAA authorization, a legal representative may sign for the subject. A copy of the signed consent form will be given to the subject or legal representative of the subject and the original will be maintained with the subject's records.

16.4 Publications

The preparation and submittal for publication of manuscripts containing the study results shall be in accordance with a process determined by mutual written agreement among the study Sponsor and participating institutions. The publication or presentation of any study results shall comply with all applicable privacy laws, including, but not limited to, the Health Insurance Portability and Accountability Act of 1996.

16.5 Investigator Responsibilities

By signing the Agreement of Investigator form, the Investigator agrees to:

1. Conduct the study in accordance with the protocol and only make changes after notifying the Sponsor (or designee), except when to protect the safety, rights or welfare of subjects.
2. Personally conduct or supervise the study (or investigation).
3. Ensure that the requirements relating to obtaining informed consent and IRB review and approval meet federal guidelines, as stated in § 21 CFR, parts 50 and 56.
4. Report to the Sponsor or designee any AEs that occur in the course of the study, in accordance with §21 CFR 312.64.
5. Ensure that all associates, colleagues and employees assisting in the conduct of the study are informed about their obligations in meeting the above commitments.
6. Maintain adequate and accurate records in accordance with §21 CFR 312.62 and to make those records available for inspection with the Sponsor (or designee).
7. Ensure that an IRB that complies with the requirements of §21 CFR part 56 will be responsible for initial and continuing review and approval of the clinical study.

8. Promptly report to the IRB and the Sponsor (or designee) all changes in the research activity and all unanticipated problems involving risks to subjects or others (to include amendments and IND safety reports).
9. Seek IRB approval before any changes are made in the research study, except when necessary to eliminate hazards to the patients/subjects.
10. Comply with all other requirements regarding the obligations of clinical investigators and all other pertinent requirements listed in § 21 CFR part 312.

APPENDIX 1. STUDY VISITS

	SCREENING	VISIT 1 (CLINIC VISIT, DAY 0) ^a	VISIT 2 (PHONE CALL, DAY 5) ^a	VISIT 3 (OPTIO NAL CLINIC VISIT, DAY 7- 14) ^a	VISIT 4 (PHONE CALL, DAY 14) ^a	VISIT 5-10 (STARTING 1 MONTH AFTER LAST DAXI INJECTION, MONTHLY UNTIL LOSS OF BENEFIT)
Informed Consent	X					
Medical History	X					
Urine pregnancy test (if applicable)		X				
Physical Exam		X				
DAXI Injection		X		X		
USDRS		X		X		
Phone call to assess duration of benefit			X		X	X
EAT-10	X		X		X	
VHI-10	X				X	X
OMNI-VES	X				X	X
CPIB-10	X				X	X
Phonalyze recording	X				X	X

^a ±2 days

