	
wear off and the sometimes challenging access to treatment, a longer acting agent is desire.
 
Injectable daxibotulinumtoxinA (DAXI, Revance Therapeutics Inc., Newark, CA) is a FDA-approved botulinum toxin type A indicated for the treatment of glabellar lines. It has been shown in large clinical trials to provide safe, effective treatment for cervical dystonia and may offer longer-lasting results when compared with onabotulinumtoxinA.
 
Thus, a study examining the effect of DAXI for patients with adductor laryngeal dystonia (ADLD) is proposed. This study aims to assess the efficacy of DAXI for transcervical laryngeal injection in patients with adductor laryngeal dystonia.

STUDY DESIGN	A single-arm, open-label, dose-escalation phase 4 study.
PRIMARY OBJECTIVE	Determine the efficacy of DAXI for treatment of ADLD.
SECONDARY OBJECTIVES	Compare duration of benefit between DAXI and BotoxA.
NUMBER OF SUBJECTS	20

SUBJECT SELECTION CRITERIA	
Inclusion Criteria:
 
Age ≥ 18
 
Diagnosis of adductor laryngeal dystonia (ADLD)
 
Previous successful treatment with BotoxA and stabilized dose for the last 3 treatments
 
Acceptable form of birth control for females of childbearing potential.
 
Women of childbearing age must have a negative pregnancy test
 
Female participants of childbearing potential may be enrolled in the study if the participant fulfills all the inclusion criteria listed in the subject selection section below.
 
Exclusion Criteria:
 
Age < 18
 
Other neurologic conditions (ALS, Parkinson's disease, essential tremor, Meige syndrome, etc.)
 
Pregnant, breastfeeding, or unwilling to practice birth control during participation in the study.
 
Presence of a condition or abnormality that in the opinion of the Investigator would compromise the safety of the patient or the quality of the data.
 
Naive from other types of Botox for 6 months including BotoxA

TEST PRODUCT, DOSE, AND ROUTE OF ADMINISTRATION	
Open-label dose of DAXI injected at either 0.625, 1.25, or 2.5 units. Dosage will be determined by subject's previous stabilized Botox dosage.

CONTROL PRODUCT, DOSE AND ROUTE OF ADMINISTRATION	N/A
DURATION OF SUBJECT PARTICIPATION AND DURATION OF STUDY	Subjects will be in the study for up to 36 weeks. Total time for recruitment and completion of the study will be up to 2 years.
CONCOMMITANT MEDICATIONS	Allowed: all Prohibited: Other forms of Botox

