4 STUDY DESIGN

4.1 Study Overview

This is a single-center, open-label, dose-escalation trial. 20 subjects are planned. Each subject will be administered a single dose of DAXI. If the subject does not achieve the desired self-reported voice improvement, at 1 week post injection an additional dose of DAXI will be administered.

Screening data will be reviewed to determine subject eligibility. Subjects who meet all inclusion criteria and none of the exclusion criteria will be entered into the study.

The following treatment regimens will be used:

- Injection of DAXI at the following doses: 0.625, 1.25, 2.5 units depending on subject's current standard dose of Botox.

Total duration of subject participation will be 36 weeks. Total duration of recruitment and completion of all procedures of the study is expected to be up to 2 years.

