5.2 Secondary Efficacy Endpoints

The secondary endpoint is duration of benefit, assessed by median time to baseline VHI-10 after treatment with DAXI and via phone call surveys. VHI-10 questionnaires will be given at baseline, day 14, then monthly until loss of benefit. Phone calls will be conducted at day 5, day 14, then monthly until loss of benefit.

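### The end of follow-up is stated in three conflicting ways; if the visit numbering is followed, duration data stop about 26 weeks after the last injection and the powered duration comparison can lose most of its power.

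*Combined protocol and SAP*

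**What the plan says.** Three statements govern how long duration of benefit is observed.

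- **Visit numbering.** Section 9.6 covers Visits 5-10, described as "Remote Survey, every month starting 1 month after most recent injection". Appendix 1 has the same six visits: "VISIT 5-10 (STARTING 1 MONTH AFTER LAST DAXI INJECTION, MONTHLY UNTIL LOSS OF BENEFIT".
- **Open-ended rule.** Section 9.6 also says "Data is collected monthly until loss of benefit", and Section 5.2 says "VHI-10 questionnaires will be given at baseline, day 14, then monthly until loss of benefit". Neither gives a last month.
- **Length of participation.** Section 4.1: "Total duration of subject participation will be 36 weeks". The synopsis: "Subjects will be in the study for up to 36 weeks".

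Sections 14.3 and 14.4 plan a Kaplan-Meier curve, and 14.4 adds a median time to baseline VHI-10. Section 14.6 powers a difference in mean duration against prior Botox, using this input: "Unpublished data from our institution revealed an average duration of 18.9 weeks with a standard deviation of 7.2 weeks". None of these sections says how a subject who still has benefit at the last contact is handled, or whether duration runs from the first or the last injection.

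**The concern.** The secondary objective (Section 3.2) is whether DAXI lasts longer than Botox, and Section 14.3 also lists duration as a further primary outcome. The last numbered survey falls about one SD above the institution's Botox mean (18.9 + 7.2 = 26.1 weeks). Subjects whose benefit outlasts it are the ones who would show that DAXI lasts longer.

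A coordinator working from the visit table has no scheduled contact after Month 6. One working from the open-ended rule keeps calling, with no stated end. One working from Section 4.1 stops at 36 weeks. Subjects could therefore be followed for different lengths of time under the same protocol, and late data that were not collected cannot be recovered.

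**Working it through.** **Inputs.** From Section 14.6: Botox mean 18.9 weeks, SD 7.2, planned difference 2.4 weeks, n = 20, within-subject correlation 0.875. From Section 9.4: optional second injection on Day 7-14. From Section 9.1: screening 7 days before injection. Assumed: normal durations with the same SD for DAXI, no dropout, monthly spacing of the surveys ignored, and two-sided alpha 0.05 (the plan states alpha for VHI-10 only, without sidedness).

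**1. The plan's own figure.** SD of the paired difference = 7.2 × √(2 × (1 − 0.875)) = 3.60. Noncentrality = 2.4 / (3.60/√20) = 2.98. Power of the paired t-test is 80.7%, so the stated 80% reproduces.

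**2. Calendar.** One month = 365.25/12/7 = 4.348 weeks. Weeks from the first injection:

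| Injections | Month 6 | Month 7 | Month 8 |
|---|---|---|---|
| One | 26.1 | 30.4 | 34.8 |
| Second on Day 7 | 27.1 | 31.4 | 35.8 |
| Second on Day 14 | 28.1 | 32.4 | 36.8 |

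Add one week to each if screening counts towards participation. Month 6 falls 36 − 26.1 = 9.9 weeks short of 36 weeks after one injection, and 36 − 28.1 = 7.9 weeks short after a second on Day 14 (screening not counted).

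**3. Share still benefiting at the last survey.** P(T > c) = 1 − Φ((c − m)/7.2). At the planned effect, m = 18.9 + 2.4 = 21.3:

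- c = 26.09: z = 0.665, share 25%
- c = 34.79: z = 1.87, share 3%
- c = 36: z = 2.04, share 2%

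A lognormal shape gives 22% at 26.1 weeks and 4% at 36.

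**4. Effect on the mean difference, if only DAXI durations are capped.** E[min(T, c)] = mΦ(z) − 7.2φ(z) + c(1 − Φ(z)).

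- At m = 21.3 and c = 26.09: 21.3 × 0.747 − 7.2 × 0.320 + 26.09 × 0.253 = 20.21. Minus 18.9, this leaves 1.31 weeks of the true 2.4.
- With no true difference (m = 18.9), the same cap gives 18.30 − 18.9 = −0.6 weeks, against DAXI.

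**5. Effect on power, same assumption.** Simulated paired t-test, correlation 0.875, true gain 2.4 weeks:

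| Cap on DAXI duration | Power |
|---|---|
| None | about 81% |
| 26.1 weeks | about 31% |
| 34.8 weeks | about 78% |
| 36 weeks | about 79% |

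**6. Kaplan-Meier median.** With no dropout, it is not reached by week c if at least 11 of 20 durations exceed c (binomial, using the shares from step 3).

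| True gain | Share beyond 26.1 weeks (normal) | Median not reached: normal | Median not reached: lognormal |
|---|---|---|---|
| +2.4 weeks | 25% | 0.4% | 0.1% |
| +6 weeks | 43% | 21% | 9% |
| +8 weeks | 54% | 57% | 39% |

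With follow-up to 36 weeks the chance is about zero in every row.

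**The case against.** The strongest reply is that no passage ends collection at Visit 10 for a subject who still has benefit. The header that numbers the visits carries the open-ended rule, Sections 5.2 and 9.6 repeat it, and 36 weeks of participation points to longer follow-up. The payment cap also allows 15 paid entries ($150 / $10), more than the eight full sets in the numbered schedule, though that is weak evidence. All of this stands. A reader might infer from the numbering that follow-up is fixed to end at 26 weeks. The documents do not support that, so every loss shown here is conditional on the six-visit reading.

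A reader might also infer that the median duration cannot be estimated. The planned endpoint is a Kaplan-Meier median, which allows for right-censoring. Even a hard stop at 26.1 weeks leaves it unreached in under 0.5% of trials at the planned effect. It comes under threat only if DAXI outlasts Botox by about 6 weeks or more.

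Third, the drop to 1.3 weeks and 31% power needs an analysis that the plan does not specify: DAXI durations truncated, prior Botox durations not. If both were truncated, the difference would be 20.21 − 18.30 = 1.9 weeks, a smaller loss. That is fair. The calculation illustrates what the missing censoring rule permits and does not predict what the analyst will do. It remains relevant because Section 14.6 powers a difference in means, and nothing says how incomplete durations enter one.

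**Conclusion.** The point holds as an internal contradiction with a conditional cost. The visit numbering, the open-ended rule and the 36-week participation give three different ends of follow-up, and only the first has numbered visits behind it.

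Under the six-visit reading, about a quarter of subjects at the planned effect are censored at Month 6. The main exposure is the mean comparison powered in Section 14.6, with power of about 31% in place of about 81% if DAXI durations alone are truncated. The median is safe at the planned effect. Follow-up to 34.8-36 weeks removes nearly all of the loss.

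The contradiction can be read directly from the text. The sizes rest on the assumptions listed with the calculation, mainly the duration shape, an SD for DAXI equal to that for Botox, and the one-sided truncation.

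**What to change.** Reconcile Section 9.6, Appendix 1, Section 4.1 and the synopsis around one end of follow-up.

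- **Visits.** Extend the numbered remote surveys to the stated 36 weeks for subjects still benefiting. After a single injection, Months 7 and 8 fit, even with the screening week counted (34.8 + 1 = 35.8).
- **Re-injected subjects.** Month 8 after a second injection on Day 14 is at week 36.8 from the first injection. After one on Day 7 it is at 35.8, or 36.8 with screening. Where Month 8 overruns, end at Month 7 or make a final contact at week 36; otherwise align the 36-week statement with Month 8.
- **Time origin.** State whether the 36 weeks include screening, and whether duration of benefit runs from the first or the last injection.
- **Analysis.** In Section 14.4, treat subjects still benefiting at the last contact as administratively censored at that contact, not as having lost benefit then. Say how censored durations enter any comparison with prior Botox.

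The cost is a text amendment and at most two more remote surveys per subject still benefiting. Paid sets rise from 8 (screening, Day 14, six monthly) to at most 10, or 10 × $10 = $100, within the $150 cap. No dose or treatment rule changes.
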